1. STATEMENT OF COMPLIANCE

The trial will be carried out in accordance with International Conference on Harmonisation Good Clinical Practice (ICH GCP) and the following:

- United States (US) Code of Federal Regulations (CFR) applicable to clinical studies (45 CFR Part 46, 21 CFR Part 50, 21 CFR Part 56, 21 CFR Part 312, and/or 21 CFR Part 812)

The protocol, informed consent form(s), recruitment materials, and all participant materials will be submitted to the Institutional Review Board (IRB) for review and approval. Approval of both the protocol and the consent form must be obtained before any participant is enrolled. Any amendment to the protocol will require review and approval by the IRB before the changes are implemented to the study. In addition, all changes to the consent form will be IRB-approved; a determination will be made regarding whether a new consent needs to be obtained from participants who provided consent, using a previously approved consent form.

1 PROTOCOL SUMMARY

1.1 SYNOPSIS

Title:	A prospective, randomized, single-blinded superiority study to evaluate bone wax use for hemostasis during primary unilateral total knee arthroplasty
Study Description:	
Total joint arthroplasty can result in significant blood loss. Postoperative anemia has been associated with prolonged length of stay and increased hospital costs.¹ Minimizing blood loss has led to multiple blood conservation strategies in orthopaedic procedures.
 
Bone wax is a well-known topical hemostatic agent comprised of a mixture of beeswax, paraffin, and isopropyl palmitate. This inexpensive agent works by sealing the bleeding site and tamponades bleeding from the cancellous bone. Bone wax can be precisely applied evenly and stops bone bleeding immediately upon application.²
 
The purpose of this study is to assess whether the application of bone wax to exposed cancellous bone, after the cemented implants are in place, will provide superior hemostasis in total knee arthroplasty (TKA) patients compared to patients who do not have the bone wax applied. Hemostasis will be assessed by calculating blood loss using the Hb-balance formula.

	
This will be a prospective, randomized, single-blinded, superiority study in patients scheduled for a primary unilateral TKA with [name] or [name]. The restriction of this study to two surgeons will limit variations in the outcomes being measured due to differences in surgical technique.

Objectives:	
Primary Objective:
 
• Efficacy: To assess whether bone wax results in superior hemostasis in patients undergoing primary unilateral TKA• Safety: To compare the safety profile between the 2 cohorts 
Secondary Objective:
 
• To assess whether the objective and functional outcomes in patients undergoing primary unilateral TKA differ between the patient cohorts (use of bone wax vs no bone wax)• To assess if there is a difference in the reduction of the Hemoglobin (Hgb) and Hematocrit (Hct) between the patient cohorts
Endpoints:	
Endpoints-Primary:
 
• Efficacy: To calculate estimated perioperative blood loss on POD 1 using the Hb-balance formula• Safety: To assess the patients for any device adverse events related to the use of bone wax 
Endpoints-Secondary:
 
• To calculate the Knee Society Scores (KSS), both objective and subjective scores, done preoperatively and 8 weeks postoperatively• To measure the difference between the preoperative and POD1 Hemoglobin (Hgb) and Hematocrit(Hct) values in the two patient cohorts

Study Population:	100 female and male patients (50 subjects in each arm) scheduled for unilateral total knee arthroplasty by Drs. [name] or [name]
Phase:	NA
Description of Sites/Facilities Enrolling Participants:	Department of Orthopaedics, Syosset Hospital
Description of Study Intervention:	Bone wax is a well-known topical hemostatic agent comprised of a mixture of beeswax, paraffin, and isopropyl palmitate. This inexpensive agent works by sealing the bleeding site and tamponades bleeding from the exposed cancellous bone. ²
Study Duration:	The study timeline is 18 months
Participant Duration:	Patients will be in the study from the date of consent until their 8 week postoperative visit.

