The limitations in the Moo et al. study were, they did not collect postoperative outcomes such as pain, range of motion, and Knee Society Score (KSS). Efficacy and safety data are lacking in this publication as most patients were transferred to a rehabilitation facility. Long term follow-up on clinical outcomes such as range of motion and functional assessment scores were not reported. The study subjects consisted of patients with osteoarthritis of the knee only, thereby, excluding whether patients with other inflammatory arthritis may benefit from the use of bone wax. The use of a chemical hemostatic agent tranexamic acid (TXA) was also excluded from the surgical procedure. The incorporation of TXA could have increased the level of hemostasis.

A recently published manuscript by Shin, et al also evaluated blood loss outcomes with the use of bone wax. Though this study also found bone wax reduced blood loss there were several limitations to the study. First, its retrospective design is inherently disadvantageous. Second, the postoperative outcomes such as pain score, range of motion, length of stay and clinical scores, were not compared between the groups. Third, although there was no significant intergroup difference in the radiologic prosthetic coverage of the osteotomy surface, the area of the cancellous bone surface uncovered by the femoral and tibial components were not evaluated intraoperatively. The area of residual osteotomy might be associated with the volume of blood loss and consequently with transfusion rates because osseous hemorrhage is one of the main bleeding sources.⁵

The investigators would like to address limitations in these studies by conducting a prospective, randomized trial. This study will also be collecting outcome measures (Knee Society Score) which were noted limitations of these studies. Additionally, the surgeons will be measuring the amount of exposed cancellous bone in the OR. The method to be used is referenced in this protocol.

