2.3 RISK/BENEFIT ASSESSMENT

2.3.1 KNOWN POTENTIAL RISKS

The surgical techniques used to promote hemostasis will be consistent for all patients, except for the use of bone wax applied to the exposed cancellous bone following insertion of the prosthesis. There is a potential that patients in the control arm could have increase bleeding. The following risks have been shown to be associated with the use of bone wax: failed bone healing, foreign body reaction, granuloma growth, thrombosis, infection, and nerve compression

There is a small risk of an unintended breach of confidentiality, as there is in any research study that collects subjects' health information.

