2.3.3 ASSESSMENT OF POTENTIAL RISKS AND BENEFITS

Shin and Moo have published on the use of bone wax in total knee arthroplasty, 296 and 50 patients respectively had bone wax used during their total knee replacement. Shin, et al found that no adverse reactions, including the development of infections or foreign body reactions, were observed after the application of bone wax, a finding consistent with those of Moo et al.⁵

Moo found the difference between the bone wax group and the control group with regards to transfusion requirements and adverse events following surgery did not reach significance with the numbers available; however, trends in favor of the use of bone wax were noted.²

Drs. [name] and [name] have been using bone wax on exposed cancellous bone for over 4 years. All surgical site infections are reported as part of the Northwell Health System quality metrics. Bone wax has been used in 1140 total knee procedures. For this time period superficial

infections were reported in 2 patients and 1 deep infection. Additionally, the surgeons have not had any other issues felt to be related to the bone wax in their patients during their long term follow-up visits. The surgeons technique is to apply the bone wax to the exposed cancellous bone after the implant has been cemented in place therefore eliminating the risk for any issues with bone ingrowth.

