3 OBJECTIVES AND ENDPOINTS

OBJECTIVES	ENDPOINTS	JUSTIFICATION FOR ENDPOINTS

Primary
 
• Efficacy: To assess whether bone wax results in superior hemostasis in patients undergoing primary unilateral TKA• Safety: To compare the safety profile between the 2 cohorts	
• To calculate estimated perioperative blood loss on POD 1 using the Hb-balance Formula• To assess the patients for any device adverse events related to the use of bone wax	
Use of the Hb-balance Formula provides a more accurate assessment of blood loss
 
To ensure there are no safety issues between the two cohorts

Secondary	
• To assess whether objective and functional outcomes in patients undergoing primary unilateral TKA differ between the two patient cohorts• To determine if there is a difference in blood loss between the two cohorts 
• To calculate the Knee Society Scores, both objective and subjective scores, done preoperatively and 8 weeks postoperatively• To measure the difference between the preoperative and POD1 Hemoglobin (Hgb) and Hematocrit (Hct) values in the two patient cohorts	
The Knee Society Score is a validated tool to assess both objective and subjective outcomes. The collection of the KSS is a standard of care for Drs. [name] and [name]'s TKA patients.
 
These values will be used to assess hemostasis over time

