Intraoperative blood management strategies will be consistent for all subjects to avoid any confounding factors which could affect postoperative transfusion requirements. Any patients unable to be treated according to the department treatment guidelines will be excluded from the study. Intraoperatively blood loss is minimized by anesthetic techniques, pharmacologic interventions, and surgical techniques, as per standard of care and department treatment guidelines.

The patient and the postoperative hospital staff will be blinded to the treatment arm. The OR staff will be trained not to discuss this information with the patient. During the transition of care from the OR to the Post Anesthetic Care Unit (PACU) the use of bone wax is not routinely included in the verbal patient report. The lack of this information is not required to effectively manage the patient in the postoperative period and will not affect patient care. Postoperatively medical care is managed by the hospitalist, medical doctors specializing in the care of hospitalized patients. Hgb and Hct are drawn daily during the patient's hospitalization as per the standard of care. These values will be used to calculate the Hb-balance Formula.

Blood loss will be calculated using the Hb-balance Formula. This method is being used to provide a more standardized method of calculating blood loss. Eipe and Ponniah showed that surgical blood loss was underestimated by 64% when clinical methods are used to assess blood-soaked sponges and blood lost to suction bottles and the vacuum drain.⁷

Following discharge patients will be followed in the outpatient surgical office according to the postoperative standard of care visit schedule. Results of the 2011 KSS Objective and Functional Outcome Measurements administered as part of standard of care at the 8 week postoperative visit, or the office visit closest to these time points will be collected for research purposes. Patients will be called at 56 days (+2weeks) from the date of surgery for any device related adverse events. This call is standard of care for the department. Three attempts will be made to reach the patient before they are considered "lost to follow-up".

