8.2 SAFETY AND OTHER ASSESSMENTS

8.3 ADVERSE EVENTS AND SERIOUS ADVERSE EVENTS

8.3.1 DEFINITION OF ADVERSE EVENTS (AE)

Adverse event means any untoward physical or psychological occurrence in a human subject participating in research. An AE can be any unfavorable or unintended event including abnormal laboratory finding, symptom or disease associated with the research or the use of a medical investigational test article.

Medical Device Reporting:

This clinical trial is evaluating a commercially available marketed product. This product is being used according to the manufacture's guidelines.

This study will adhere to the adverse event reporting regulations of the Centers for Devices and Radiological Health (CDRH), part of the Food and Drug Administration (FDA) regulations. In accordance with the Safe Medical Devices Act of 1990 (SMDA) (Public Law 102-629) (21 CFR 803.32 (c)) ambulatory surgery centers, hospitals, outpatient diagnostic centers and other user facilities are required to report all incidents in which a medical device or user error may have caused or contributed to the death, serious injury or serious illness of a patient.

Adverse Event Reporting Period

The study period during which adverse events must be reported is defined as the period from the application of the bone wax to the end of the study treatment follow-up.

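### The safety endpoint is justified as ensuring there are no safety issues, but 50 wax patients, descriptive reporting and about 8 to 10 weeks of observation can support only a time-limited description

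*Combined protocol and SAP*

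**What the plan says.** Safety stands beside efficacy as a primary objective in the synopsis (section 1.1) and in section 3. The objective is to compare the safety profiles of the two arms. The endpoint is device adverse events related to bone wax, with no time point attached. The justification column of section 3 gives the reason for that endpoint: "To ensure there are no safety issues between the two cohorts".

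Section 2.3.1 lists the risks associated with bone wax: "failed bone healing, foreign body reaction, granuloma growth, thrombosis, infection, and nerve compression". It gives no rate and no onset time for any of them.

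On duration, the synopsis says "Patients will be in the study from the date of consent until their 8 week postoperative visit". Section 4.2 adds a later contact: "Patients will be called at 56 days (+2weeks) from the date of surgery for any device related adverse events". The Schedule of Activities (section 1.3) gives that call its own column after the 8-week visit and marks device adverse events for collection there. Section 4.4 defines completion by the last visit or procedure in that schedule. Section 8.3.1 defines the reporting period as "the period from the application of the bone wax to the end of the study treatment follow-up", and that end is not defined further.

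On analysis, section 9.4.4 plans descriptive reporting because few events are expected. Section 8.3.5 says that no event related to wax application will occur in the control group.

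**The concern.** The justification asks for an assurance that safety issues are absent. Fifty wax patients followed for about 8 to 10 weeks cannot supply one. As worded, an uneventful trial could be read as having met a primary safety aim, when the data would exclude only fairly large risks and only for events that had appeared by the last contact.

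The window also lacks a stated rationale. Nothing in the plan explains why 8 weeks suits the risks in section 2.3.1. For its own reassurance, section 2.3.3 draws on a longer horizon: "the surgeons have not had any other issues felt to be related to the bone wax in their patients during their long term follow-up visits". How far those visits extend is not given.

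Finally, the statements of when observation ends do not agree, so the period to which any safety result applies is not fixed.

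**Working it through.** **The plan's own figures.** No figure is given for safety. The only computed figures are the blood-loss powers in section 9.2. With 50 per arm and a two-sided 5% t-test, I obtain 79.7%, 95.4%, 82.3%, 91.0% and 80.8%, against the stated 80%, 95%, 82%, 91% and 81%. The pooled SD is √((282.7² + 259.8²)/2) = 271.49, against 271.5. These figures reproduce, but they concern efficacy only.

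**1. What zero events in the wax arm would show.** Input: n = 50 (section 9.2).
- One-sided 95% upper limit: 1 − 0.05^(1/50) = 5.8%.
- Upper end of the two-sided 95% exact interval: 1 − 0.025^(1/50) = 7.1%.

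**2. Scale from the surgeons' own record.** Section 2.3.3 reports 2 superficial infections and 1 deep infection in 1140 procedures with wax.
- Rate: 3/1140 = 0.263% (exact 95% interval 0.05% to 0.77%).
- Expected in 50 patients: 50 × 0.00263 = 0.13.
- Chance of seeing at least one: 1 − (1 − 0.00263)^50 = 12%.

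At that rate, the most likely result in the wax arm is no infection at all.

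**3. What a between-arm comparison could detect.** Fisher's exact test, 50 per arm, no events in controls:
- 5 against 0: p = 0.056.
- 6 against 0: p = 0.027.

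At least 6 wax events (12%) against none would be needed for p < 0.05. The plan specifies no such test; this shows only the size of signal that the numbers could carry. For events classed as wax-related, section 8.3.5 makes the control count zero by definition, so that comparison carries no information about excess risk at any length of follow-up.

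**4. What the window could add.** The documents give no onset times, so this is an assumed range. If r is the true cumulative risk and f the share of events that appear by the last contact, the chance of observing at least one event in 50 is 1 − (1 − rf)^50.

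| r | f = 1 | f = 0.5 | f = 0.25 | f = 0.1 |
|---|---|---|---|---|
| 1% | 39% | 22% | 12% | 5% |
| 2% | 64% | 39% | 22% | 10% |

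Even when every event appears in time (f = 1), a 2% risk would go unseen in 36% of such trials (100 − 64). The window can only lower detection from there; by how much is unknown.

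**5. When observation ends.** Eight weeks is day 56. The call is at day 56 plus up to 14 days, so about day 70, or 10 weeks. The synopsis ends participation at the visit, while sections 1.3, 4.2 and 4.4 carry it to the call. The reporting period in section 8.3.1 starts at wax application, an event that control patients do not have.

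**The case against.** A reader might go further and infer that the listed harms appear too late for an 8-week trial, so that the safety objective is unattainable because of the window. The documents do not support this. Section 2.3.1 gives no onset time for any of its six risks, and nothing places any of them after week 8. The actual objective is a comparison of safety profiles; the assurance is the justification for the endpoint.

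A reader might also take the criticism of the earlier randomized trial in section 2.2, "Long term follow-up on clinical outcomes such as range of motion and functional assessment scores were not reported", as a promise of long-term safety follow-up. That sentence concerns clinical outcomes. The same paragraph does say that safety data were lacking, but the remedies named are a prospective randomized design, the Knee Society Score and measurement of exposed bone.

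Other points in the plan's favour:
- The limits in step 1 depend on n = 50 and would be the same after longer follow-up. This stands: they measure sample size, and the window merely restricts which events they cover.
- The infection record counts all surgical-site infections over an unstated follow-up, whereas the endpoint is wax-related events. This stands; step 2 is for scale only.
- Section 9.4.4 sets no test or success rule, so nothing says an event-free trial will be declared safe. This stands, but it also means the analysis has no means of delivering what section 3 states as its purpose.
- The product is marketed and used as labelled, it has been these surgeons' practice for four years, and section 2.3.3 says application after cementing removes bone-ingrowth issues. This is relevant context, but the ingrowth point does not speak to granuloma, foreign body reaction or infection.
- Section 4.4 goes most of the way to settling the duration question. It does; what remains is a short alignment of wording.

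**Conclusion.** The concern holds as a mismatch between the stated purpose of the safety endpoint and what the design can show. With 50 wax patients, descriptive reporting and wax-related events excluded by definition in controls, the trial cannot ensure the absence of safety issues. Zero events would be compatible with a true risk of up to 5.8% (one-sided) or 7.1% (two-sided), and only for events seen by about day 56 to 70. These limits assume that all 50 are observed to the last contact; any loss to follow-up widens them.

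The 8-week window is unjustified against the listed risks, but it is not shown to be wrong. Sample size and the control-arm rule limit the safety conclusion whatever the length of follow-up. The efficacy analysis on postoperative day 1 is unaffected.

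**What to change.** 1. **Restate the safety aim.** In the synopsis and section 3, word the objective, endpoint and justification along these lines: *to describe adverse events in each arm from surgery to the last scheduled contact (8-week visit or telephone call, call window to about day 70), with exact 95% confidence intervals*. Delete the clause about ensuring there are no safety issues, add the intervals to section 9.4.4, and state that safety conclusions apply only to that window.
2. **Collect the same events in both arms.** A description by arm needs this. Section 8.3.4 asks for all adverse events regardless of relationship, section 8.3.5 leaves out expected ones, and the call in section 4.2 asks only about device-related events. Reconcile these.
3. **Align the dates.** Make the participant-duration statement in the synopsis and the reporting period in section 8.3.1 match the call in sections 1.3, 4.2 and 4.4, with a starting point that exists for controls.
4. **Optional.** Report separately, for both arms, any later events found in existing standard-of-care charts and in routine infection reporting, which section 2.3.3 describes: "All surgical site infections are reported as part of the Northwell Health System quality metrics". The sponsor should choose and justify the cut-off date.

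Items 1 and 3 cost protocol wording and any matching consent text. Item 2 may add case-report-form entries but no visits. Item 4 costs consent wording, chart-review work and possibly an extension of the 18-month study timeline, which is why it is left as a choice.

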1.2 SCHEMA

Preoperative Period	Consent
<hr/>	
	Total n=100 (50 subjects in each arm)
	Preoperative Knee Society Score
	Obtain informed consent
	Collect Baseline Laboratory Values (Standard of Care)
	Screen potential participants by inclusion and exclusion criteria
Day of Operation	Randomization
<hr/>	
	Confirm Inclusion/Exclusion Criteria
	Group 1-Bone Wax (n=50)
	Group 2-No Bone Wax (n=50)
Hospitalization	Baseline assessments/ Study Intervention
<hr/>	
	Complete Blood Count (CBC) (Standard of Care lab)
	Calculation of
	Device Adverse Event Assessment
Postoperative 8 week	Follow-up assessments of study endpoints and safety
<hr/>	
	Postoperative KSS
	Device Adverse Event Assessment
8 week follow-up phone	
<hr/>	
	Follow-up Telephone Call (Standard of Care)

1.3 SCHEDULE OF ACTIVITIES (SOA)

VISIT WINDOW	PREOPERTIVE PERIOD	DAY OF SURGERY	HOSPITALIZATION	8 WEEK PO VISIT (SOC)	2 MONTH FOLLOW-UP PHONE CALL (SOC)
CONSENT	X				
DEMOGRAPHICS	X				
PRESURGICAL TESTING HISTORY & PHYSICAL (SOC)	X				
PREOPERATIVE KNEE SOCIETY SCORE	X				
CONFIRM INCLUSION/EXCLUSION	X				
RANDOMIZATION		X			
SURGEON TO GRADE AMOUNT OF EXPOSED BONE		X			
DAILY HGB/HCT (SOC)			X		
POSTOPERATIVE KNEE SOCIETY SCORE				X	
DEVICE ADVERSE EVENTS		X	X	X	X

